- 1.Cost measures include practitionerreported mean mitigation costs for practice and office visit approaches to SC2 transmission risk mitigation. Mean reported expenditures on SC2 mitigation strategies for facility modification. equipment, and PPE use.
- 2. Mean comfort and/or confidence levels are estimated for each surveyed mitigation approach using 5point Likert scales
- 3. Changes in virus mitigation approaches (Aim 3) are assessed by comparing Wave 2 with Wave 1 data for practitioners who complete both surveys. Wave 2 survey includes questions for assessing the impact of Rapid Reports and webinars from Wave 1 on practitioner decision making.
- Changes in comfort levels are also assessed, which is relevant for respondents who may not

- 1-3. Data are collected from 2 practitioner surveys. Practice recommendation s and guidelines, and disease incidence data are collected at the time of each survey conduct.
- 4. Capability for expansion is designed into the Registry as the CORE Registry study modules are built. Integration of at least one COVID-related network study will be assessed by 2 years after completion of the CORE study.

that may be developed for change their implementation depending mitigation on approved research approach but may studies and resources. have improved confidence in the Potential future modules approaches they use. These would include: a) an SARS-CoV-2 Reporting "Dashboard" and otherwise go Risk Assessment Tool and unmeasured. Network practitioners; b) COVID-19 antigen/antibody 4. Aim 4 outcome testing and contact tracing measured as the research; c) Dental office successful staff and patient vaccination integration of one research; d) Interventions to or more additional reduce COVID-19 COVID-related transmission risks; and e) network study. Patient COVID-19 history, knowledge and mitigation practices research.

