4. STUDY DESIGN

The CORE Registry study is a cross-sectional survey administered at two time points, with comparison of response changes between the two survey periods. The study includes: a) administration of a CORE Registry Questionnaire in two waves; b) identification of common approaches used by National Dental PBRN practitioners to mitigate SARS-CoV-2 transmission risks, their costs, and assess practitioners' comfort levels with these approaches; and c) rapid reporting of survey results after each wave using research summary reports and informational webinars. Classification and Regression Tree (CART) techniques will be used to assess practitioner type, practice setting, location, and other factors associated with differences in mitigation methods, costs, and comfort levels for Waves 1 and 2, and changes between each wave.

All eligible dental practitioners at the limited or full participation level in the National Dental PBRN will be invited via email to participate in the CORE Registry study. The surveys will be administered using the electronic data capture (EDC) system on the Network HUB website, housed at the NCC.

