We use published information obtained from the CDC, ADA, OSHA, and other sources to assign each approach to a pathway and category, noting that individual approaches may apply to more than one transmission pathway.

The primary outcome measure is individual and grouped practitioner-reported mitigation approaches. There are four secondary outcome measures: 1) total and monthly expenditures for mitigation; 2) level of comfort/confidence with guidelines and mitigation approaches used; 3) changes in mitigation approach, costs, and comfort/confidence between Wave 1 and Wave 2 questionnaires; and 4) successful integration of a COVID-related X01 study.

Addressing study Objectives. Objective 1 (Primary). Identify and compare the use of recommended approaches among National Dental PBRN practitioners to mitigate SARS-CoV-2 transmission risks at dental offices, by transmission pathway and mitigation type.

We will use data from the two surveys to identify distinct combinations of risk mitigation approaches, by type and transmission pathway, used by National Dental PBRN practitioners, overall and for different practitioner subgroups. First, we will examine the frequencies of individual approaches by type and pathway, that are reported by distinct groups of practitioners. We will use these results to inform a process to combine approaches within each type and pathway among subgroups of practitioners.

For the Wave 1 questionnaire, mitigation approaches reported by participating practitioners are grouped by approach type and transmission pathway. For each type and pathway, responses to individual approach questions are classified as either dichotomous (yes/no) or ordered by frequency of performance on a 5-point Likert scale. While responses to each approach will be examined individually, we expect to grade responses as "following practice guidelines" for an individual recommended approach that has a "yes" or "always" response. If warranted, we will also consider adding the "almost always" as a following practice guidelines response. The outcome measure analyses are represented by the following individual and group level assessment of mitigation approaches:

Ind: Approach i,p,t, = f(practice setting, practice type, practice location, guideline source and last review, practitioner demographics, COVID history, mitigation costs, work hours, patient volume)

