Grouped: Rec Approach _{i,p,t}, = f(practice setting, practice type, practice location, guideline source and last review, practitioner demographics, COVID-19 history, mitigation costs, work hours, patient volume)

where i = individual approach, p = pathway, and t=approach type; and Rec Approach is a dichotomous (yes/no) variable for each approach recommended approach that is followed, indicated as "yes" or "always", by type and pathway. A yes to all recommendations receives a score of "1" and all other combinations receive a "0."

First, we will examine the frequencies of individual approaches by type and pathway, that are reported by distinct groups of practitioners. We use these results to inform a process to combine approaches within each type and pathway among subgroups of practitioners. We will use CART analyses to identify distinct and mutually exclusive groups of practitioners using common sets of recommended mitigation approaches.

The grouped level analysis is speculative. We will compare the correspondence with the group-level model results with individual-level model results using appropriate statistical methods.

Objective 1 (secondary). Estimate mean total fixed and monthly expenditures to mitigate SARS-CoV-2 transmission risk, overall and for mutually exclusive groups of practitioners identified by the primary objective analysis

We will estimate mean reported total and monthly recurring expenditures and 95% confidence intervals for SC2 mitigation approaches, overall and by type (FAC, STAFF, VISIT, PPE) and pathway (P2S, S2P, S2S, P2P). We will then evaluate mean expenditures and CIs for groups of practitioners identified in Objective 1.

Objective 2 (secondary): Assess mean levels of comfort and/or confidence with available information and guidelines for infection control, approaches used to mitigate SARS-CoV-2 transmission risks, and the financial impact of mitigation, overall and for mutually exclusive groups of practitioners identified by the primary and secondary objective analyses.

We use 5-point Likert scales to estimate practitioners' mean comfort and/or confidence levels for select mitigation guidelines, type, and pathway. We estimate mean comfort levels for each group of practitioners identified in the Objective 1 analysis.

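### If the CART groups are split on mitigation spending, the mean costs later reported for those groups will partly reflect the split

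*Protocol*

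**What the plan says.** Protocol 11.2 writes the primary analysis as two model lines. The individual line explains use of an approach by practice setting, type and location and then by "guideline source and last review, practitioner demographics, COVID history, mitigation costs, work hours, patient volume". The grouped line, for following every recommendation of a given type and pathway, ends in the same way: "guideline source and last review, practitioner demographics, COVID-19 history, mitigation costs, work hours, patient volume".

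The groups come from trees: "We will use CART analyses to identify distinct and mutually exclusive groups of practitioners using common sets of recommended mitigation approaches".

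Expenditure is also an outcome. Section 11.2 states: "There are four secondary outcome measures: 1) total and monthly expenditures for mitigation; 2) level of comfort/confidence with guidelines and mitigation approaches used". Secondary Objective 1 asks for mean expenditure "overall and for mutually exclusive groups of practitioners identified by the primary objective analysis", and its method reads: "We will then evaluate mean expenditures and CIs for groups of practitioners identified in Objective 1". Section 3.2 describes the cost measure as money reported as spent, beginning "Mean reported expenditures on SC2 mitigation strategies for facility modification" and going on to equipment and PPE. Section 4 likewise has CART look for "other factors associated with differences in mitigation methods, costs, and comfort levels for Waves 1 and 2, and changes between each wave".

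Nothing in the protocol takes costs out of the trees before the cost analysis, uses a separate sample for it, or mentions the overlap.

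**The concern.** A CART terminal node is defined by its predictors. If one of the cuts is a threshold on spending, the nodes on either side have different mean spending because of where the cut fell. The group means would be correct descriptions of those nodes. A reader of Secondary Objective 1, however, would take them as the cost of belonging to a group with a given mitigation pattern. Confidence intervals computed as if the groups had been fixed beforehand would not show that the same cost values chose the groups.

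There is a related problem for the primary objective. The survey asks what has been spent, and spending on facilities, equipment and PPE largely follows from having adopted the corresponding measures. A split on spending therefore partly restates the outcome and may take the place of splits on setting, practice type or region, which the study wants to find.

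**Working it through.** **Plan's own figure.** Section 5 gives about 5,300 eligible practitioners and a 38% target: 0.38 × 5,300 = 2,014. This agrees with the figure of about 2,000 in the sample size text of Section 11.1. The 80% power stated there cannot be reproduced without an effect size, intraclass correlation or group sizes, but this point does not depend on it.

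**Main simulation.** Inputs from the protocol: n = 2,014; two-sided 0.05; nodes as small as 15 (Section 11.1 mentions subgroups of 10 to 15). All other inputs are assumptions:
- a yes/no outcome (follows all recommendations), about 41% yes;
- six other predictors, independent of cost;
- log-normal cost with log-SD 1;
- a Gini tree of depth at most 4;
- 300 runs per row.

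The association of cost with the outcome was set at log-odds 0, 0.2 or 0.4 per SD of log cost. The corresponding true ratios of mean cost, followers to non-followers, are 1.00, 1.21 and 1.44. Each tree was grown with cost among the predictors and again without it. Log cost was then compared across terminal nodes by one-way ANOVA, and the ratio of highest to lowest node mean cost was recorded.

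| Log-odds (true ratio) | Stopping rule | Tree splits on cost | ANOVA p < 0.05, cost in / out | Median node ratio, cost in / out |
|---|---|---|---|---|
| 0 (1.00) | fully grown, min 15 | 90% | 91% / 6% | 11.7 / 2.0 |
| 0 (1.00) | 0.5% gain, min 15 | 17% | 20% / 6% | 1.2 / 1.2 |
| 0 (1.00) | 1% gain, min 50 | 0% | 3% / 4% | 1.1 / 1.1 |
| 0.2 (1.21) | fully grown, min 15 | 99.7% | 99.7% / 5% | 19.9 / 1.9 |
| 0.2 (1.21) | 0.5% gain, min 15 | 83% | 84% / 4% | 6.0 / 1.2 |
| 0.2 (1.21) | 1% gain, min 50 | 25% | 29% / 4% | 1.1 / 1.1 |
| 0.4 (1.44) | fully grown, min 15 | 100% | 100% / 9% | 28.8 / 2.0 |
| 0.4 (1.44) | 0.5% gain, min 15 | 100% | 100% / 8% | 13.2 / 1.2 |
| 0.4 (1.44) | 1% gain, min 50 | 98% | 98% / 4% | 5.5 / 1.1 |

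The fair comparison is cost in against cost out within a row. A highest-to-lowest ratio over several nodes exceeds 1 by chance, and reaches about 2 in fully grown trees even without cost. Where trees usually split on cost, the node ratio is several times that benchmark and well above the true ratio. Where they rarely or never do, it is about the same as with cost left out.

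**Second simulation, root split only.** Here n = 2,014, with 500 datasets per scenario. Cost competes with one two-level setting, other spending has log-SD 0.8 to 1.2, and every user of the approach incurs a fixed extra cost.
- Extra cost 25% of median other spending, use 45% v 55% by setting: cost took the root split in 100% of datasets. The two groups' mean costs differed 4.9-fold to 12.7-fold, although users truly spent 1.12 to 1.18 times as much as non-users.
- Same extra cost, 15- or 20-point setting difference: 96% to 100%.
- Extra cost 10% of the median, 20-point difference: 0% to 3%.
- Extra cost 25%, 20-point difference, reporting error of log-SD 0.5 added: 28%, 41% and 71% at log-SD 0.8, 1.0 and 1.2. At a 10-point difference it was still at least 99%.

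In the error-free version the cut isolates roughly the lowest 8% to 10% of spenders, so the large fold differences compare a small tail with everyone else.

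**The case against.** The strongest objection concerns what the groups are. The sample size text in Section 11.1 describes the primary aim as finding non-overlapping combinations of approaches, and then the characteristics associated with them. If the groups are defined by the approaches used, cost does not define them and cost by group is not circular. This reading is open. The sentences in 11.2 speak of groups of practitioners identified by CART, which favours terminal nodes, but the protocol does not settle it.

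Second, Section 3.2 gives a reason to relate cost to approach: expense may influence what practices choose. That supports examining the association. It does not support summarising cost over groups cut on cost, and what the survey records is spending, not the price faced. Being a predictor in one analysis and an outcome in another is not in itself an error.

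Third, Section 11.1 disclaims hypothesis testing and 11.2 calls the grouped analysis speculative. This lowers the stakes. Even so, a descriptive mean can mislead when the group was formed on the same variable, and the Protocol Summary says that cost differences associated with practice and practitioner characteristics will be evaluated.

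A reader might infer more: that the tree is bound to split on spending, so that the group cost differences are an artefact by construction. The documents do not support that. The protocol gives no stopping rule, which an SAP may set, and no figure for how closely spending tracks adoption. Several listed measures, such as screening or patient flow changes, may cost little. A reader might also expect the primary model to lose respondents because costs are the last of the five survey sections in 3.1. No break-off rate is given, and 11.2 allows incomplete questionnaires and possible imputation, so nothing can be concluded there.

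**Conclusion.** The point holds conditionally. The protocol places reported spending among the predictors in both primary model lines and then summarises spending over the groups that CART identifies. If those groups are terminal nodes, whenever a tree splits on spending the by-group cost result is partly produced by the cut, its intervals ignore that selection, and the split partly restates adoption.

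The frequency cannot be derived from the protocol: across the assumptions tried it ran from 0% to 100% of trees. The fold differences show direction and possible scale and are not estimates for this study. They rest on assumed cost distributions, cost shares, associations and stopping rules. Overall mean expenditure and means by type and pathway are unaffected; only the by-group cost summary and any cost-driven splits are touched. This should be fixed, but it does not undermine the study as a whole.

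**What to change.** In 11.2, leave mitigation costs out of the predictors of the trees that define the groups used in Secondary Objective 1, or state that those groups are defined by the approaches used alone. Then estimate expenditure by group with cost as an outcome only. State in either case whether a group is a terminal node or a set of approaches.

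The link between cost and approach raised in Section 3.2 can still be shown as expenditure by approach used, or in a supplementary tree that includes cost but whose groups are not used for cost comparisons.

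This is a change of wording around two model lines plus a clarifying sentence. It needs no new data and adds nothing to the questionnaire.

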3.2 Secondary

|--|

•

- 1. Secondary objective 1-:
 Estimate mean total fixed and monthly expenditures to mitigate SARS-CoV-2 transmission risk, overall and for mutually exclusive groups of practitioners identified by the primary objective analysis
- 2. Secondary objective 2: Assess mean levels of comfort and/or confidence with available information and guidelines for infection control, approaches used to mitigate SARS-CoV-2 transmission risks, and the financial impact of mitigation, overall and for mutually exclusive groups of practitioners identified by the primary and secondary objective analyses
- 3. Secondary objective 3:
 Disseminate the Wave 1
 Rapid Report and
 conduct informational
 Rapid Report Webinars
 with network
 practitioners, and assess
 the impacts of Report
 dissemination on
 changes in practitioners'
 mitigation approaches,
 mitigation costs, and
 comfort levels, overall
 and for different
 practitioner subgroups
- Secondary objective 4: Establish a modular infrastructure to support the design and conduct of additional multilevel clinical and implementation science research.

- I. The cost to dental practices for coronavirus mitigation may be significant and may influence the approaches used by practitioners and practices. PPE and other mitigation costs will be obtained via the financial costs section of the survey
- Dental care delivery creates aerosols as part of routine service delivery. Practitioner's level of comfort with treating patients with known or asymptomatic COVID-19 is an important concern that may affect their mitigation choices.

This study involves

- practitioners in the study by incorporating Rapid Results reporting and informational webinar attendance following each wave of the questionnaire. This provides an opportunity for participants to gain knowledge quickly in a rapidly changing environment, which may impact the mitigation approaches they use. We will provide Rapid Report results using the practitioner's page in the Hub, and schedule webinars to enhance discussion and support peer-to-peer information sharing. We will compare Wave 1 and Wave 2 responses to assess the impacts of the reports and webinar attendance on changes in mitigation approaches
- The CORE Registry programming and data collection capabilities will be developed to support the additional of new modules

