11.2 Final Analysis Plan

Two surveys of National Dental PBRN practitioners will be conducted to identify the approaches that practitioners and practices use to mitigate the risks of SC2 transmission for patients and dental office staff. The two surveys also collect information about sources of information and guidelines relevant to coronavirus risks and risk mitigation, practitioner-reported expenditures for mitigation (one time and recurring and monthly expenditures), weekly work hours and patient volume, and comfort or confidence levels with risk mitigation approaches and safe practice recommendations.

Participants and data.

In addition to survey data, the study team collects information on relevant practice guidelines and epidemiologic data from national and state sources, and practitioner information from the National Dental PBRN Enrollment Questionnaire (EQ).

EQ data includes practice location (region/state/county), practice setting (solo, large group, academic, community/public health), practice type (general dentist, dental specialty, dental hygienist, dental therapist), and practitioner characteristics (age, years since dental school graduation, race-ethnicity, gender, etc.).

Study measures. For this study, we separate SC2 transmission risks for dental care into four types (pathways): patient-to-staff (P2S); patient-to-patient (P2P); staff-to-patient (S2P); and staff-to-staff (S2S). Different risk mitigation approaches may address one or more pathway, but not every approach can address each pathway. We also group SC2 risk mitigation approaches into one of four categories (or types): practice facility and equipment (FAC); practitioner and staff (STAFF); Office Visits (VISIT) including patient flow and dental procedures; and personal protective equipment (PPE).

Practice-level (FAC) modifications include facility and equipment changes, patient flow redesign, and surface disinfectant procedures. Practitioner and staff (STAFF) modifications include workforce changes in hours worked and patient volume, and personnel measures to reduce or manage coronavirus exposure. Office visit (VISIT) modifications include changes to patient screening for COVID-19 and changes to aerosol generating dental procedures and techniques used. We also collect information on PPE use during dental and dental hygiene procedures, and access to PPE supplies.

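### Mitigation cost is listed as a predictor for the models that appear to form the practitioner groups, and mean cost is then reported for those same groups

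*Protocol*

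**What the plan says.** Protocol section 11.2 writes the primary outcome as a function of a predictor list, once for individual approaches and once for the grouped score. The individual-level list ends "practitioner demographics, COVID history, mitigation costs, work hours, patient volume" and the grouped list ends "practitioner demographics, COVID-19 history, mitigation costs, work hours, patient volume". Shortly after the grouped equation comes the method that forms the groups: "We will use CART analyses to identify distinct and mutually exclusive groups of practitioners using common sets of recommended mitigation approaches".

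The same section makes cost an outcome: "There are four secondary outcome measures: 1) total and monthly expenditures for mitigation". The first secondary objective estimates mean expenditure "overall and for mutually exclusive groups of practitioners identified by the primary objective analysis", and its analysis paragraph adds: "We will then evaluate mean expenditures and CIs for groups of practitioners identified in Objective 1".

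The outcome table in section 3.2 gives the reason for collecting cost: "The cost to dental practices for coronavirus mitigation may be significant and may influence the approaches used by practitioners and practices".

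No sentence keeps cost out of the trees that form the groups. None provides for sample splitting or any other allowance for selection in the intervals.

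**The concern.** A variable that helps to define a group should not then be summarised as a finding about that group. If a tree separates practitioners at some level of spending, one branch has the higher mean cost whatever approaches its members use. The table for the first secondary objective would then invite the reading that one combination of mitigation approaches costs more than another, when part or all of the gap records where the tree was cut.

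The confidence intervals do not protect against this. A standard interval for a group mean takes membership as fixed in advance. Here the boundary may have been chosen from the same data, on the variable being averaged.

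What is at stake is the by-group part of the first secondary outcome. Overall mean expenditure, and the means by mitigation type and by transmission pathway, do not depend on the trees and are unaffected.

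**Working it through.** **1. Does the text form the loop?**
- Cost is a predictor in both primary-objective equations (section 11.2).
- CART produces the mutually exclusive groups (section 11.2, after the grouped equation).
- Mean cost with a 95% interval is reported for those groups (section 11.2, first secondary objective).

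The link between the first two steps is an inference. Section 11.2 does not state that the listed function is what CART fits. Section 4 supports it, because it assigns CART the task of finding factors associated with differences in mitigation methods. The order of the text in section 11.2 points the same way.

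**2. Sample size for the illustration.** Section 5 gives about 5,300 eligible practitioners and a 38% target: 0.38 × 5,300 = 2,014. This agrees with the figure of about 2,000 in section 11.1, so n = 2,000 is used below.

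**3. Effect of one split on cost.** Let cost C be lognormal with log-mean m and log-SD s, split at its median exp(m).
- Mean above the median: 2·exp(m + s²/2)·Φ(s)
- Mean below the median: 2·exp(m + s²/2)·(1 − Φ(s))
- Ratio: Φ(s) / (1 − Φ(s))

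For s = 1: 0.8413 / 0.1587 = 5.3. For s = 1.5: 0.9332 / 0.0668 = 14. The approaches used do not enter the formula. The protocol gives no cost distribution, so both values of s are assumptions.

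**4. How often would a tree split on cost?** This was simulated with a Gini classification tree: n = 2,000, maximum depth 4, minimum leaf 15 (the upper end of the 10–15 in section 11.1), 100 runs per setting. Cost was lognormal with log-SD 1 and independent of the other predictors. The slope is the log-odds of following all recommendations per SD of log cost. The threshold is the minimum relative improvement required for a split, used as a stand-in for pruning. All settings except n and leaf size are assumptions.

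| Slope | Threshold | Runs splitting on cost | Median max/min leaf mean cost, cost included | Same, cost excluded |
|---|---|---|---|---|
| 0 | 0 | 88% | 11.4 | 2.04 |
| 0 | 0.005 | 7% | 1.06 | 1.05 |
| 0 | 0.01 | 0% | 1.00 | 1.00 |
| 0.2 | 0 | 100% | 24.8 | 2.08 |
| 0.2 | 0.005 | 94% | 5.61 | 1.03 |
| 0.2 | 0.01 | 44% | 1.00 | 1.00 |
| 0.4 | 0 | 100% | 33.6 | 1.96 |
| 0.4 | 0.005 | 100% | 15.7 | 1.02 |
| 0.4 | 0.01 | 100% | 5.45 | 1.00 |

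With cost excluded, leaves differed on log cost at p < 0.05 in 0–9% of runs. The ratio of about 2 in the unrestricted trees is noise from many small leaves.

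**5. What the ratio should be compared with.** At log-SD 1, practitioners who follow all recommendations have a mean cost about exp(slope) times that of the others: exp(0.2) = 1.2 and exp(0.4) = 1.5. At a slope of 0.4, where cost was split in every run, the leaf ratio was 5 to 34 against a true ratio between followers and others of about 1.5.

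**The case against.** **The effect is not automatic.** It needs a split on cost. With no true association, a modest threshold cut such splits from 88% of runs to 7% or 0%, and the protocol does not call for unpruned trees. This stands. A reader might infer that cost differences between groups are guaranteed by the design; the documents do not support that.

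**The groups may be defined by approaches alone.** The sentence on CART speaks of practitioners using common sets of approaches. On that reading mean cost by group is not circular. The examples of covariates in section 11.1 do not name cost, and section 4 treats cost as something to be explained. This reading is possible, but the two equations list cost explicitly and nothing excludes it. The text needs a sentence either way.

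**The analysis is descriptive.** Section 11.1 disclaims hypothesis testing, no between-group cost test is stated, and a tree that splits on cost shows the split. Section 11.2 also calls the group-level analysis speculative. This limits the harm. Group means with intervals still invite comparison, and the individual-level equation has the same predictor list.

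**Two stronger readings do not hold.** A reader might infer that hours and patient volume predict themselves for staffing outcomes, since "Practitioner and staff (STAFF) modifications include workforce changes in hours worked and patient volume". But the predictors are worded as hours and volume and the modifications as changes in them, and nothing says that either enters the score for following recommendations. A reader might also infer that cost is mainly a consequence of the approach adopted. Section 3.2 gives only the opposite direction, which is a legitimate reason to study cost as a predictor elsewhere.

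**Conclusion.** The concern holds in conditional form. As written, section 11.2 allows mitigation cost to shape the groups for which mean cost is then reported. Whenever a tree splits on cost, the by-group means partly or wholly reflect the cut, and the intervals ignore it. Section 3.2 makes such a split plausible, because the protocol itself expects cost to bear on the approaches used.

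The ratios of 5.3 and 14 and the simulated values show the mechanism. They do not estimate the error in this study, because they rest on an assumed lognormal cost, assumed slopes and assumed tree settings. The conclusion also depends on reading the listed equations as the CART models. If groups are formed from approaches alone, there is no circularity, but the protocol does not say so. The reach is limited to the by-group part of one secondary objective.

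**What to change.** In section 11.2, under the first secondary objective, state that the practitioner groups carried into the expenditure estimates come from trees fitted without mitigation costs as a predictor, or are defined by mitigation approaches alone. If cost as a driver of adoption is of interest, keep a tree that includes cost as a separately labelled analysis, and state that its groups are not used for the expenditure means and intervals.

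This needs no new data and can be done before analysis. The price is a small loss of fit in the trees that omit cost, and one extra tree if the driver analysis is kept.
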